| Marijuana: Since you last visit... (TPD - Times per day) | | MJ |
| Cigarettes: Since you last visit... (CPD) | | CPD |
| Caffeine: Since you last visit... (ozs.) | | CAFF |
| Computer Tasks: | | | | | | | | | |
| Immediate/Delayed Memory Task: Impulsivity & attention | | IMT DMT | | | | | | IMT DMT | |
| GoStop Computer Task: Response inhibition | | GoStop | | | | | | GoStop | |
| Balloon Analogue Risk Task: Risk-taking | | BART | | | | | | BART | |
| Biological Specimen Collection: | | | | | | | | | |
| Blood (plasma/serum): Hormones | BLOOD | | BLOOD | BLOOD | | BLOOD | | BLOOD | BLOOD |
| Urine: THC and Cotinine | | URINE |

Analysis Plan

Our primary outcome is change in marijuana use as defined by the TLFB at the week 4 visit relative to the baseline visit. This is a pilot study to generate data to potentially motivate and justify a future fully-powered study of PRO and marijuana cessation, so the intent of these analyses is to estimate magnitude and direction of treatment effects and associations with impulsivity (sex-specific and overall). While we expect baseline covariates to be balanced across treatment groups due to the randomization, this pilot study is small so both unadjusted and adjusted assessments of effects will be carried out by including the randomized treatment assignment and pre-specified adjusting covariates such as age, baseline progesterone, estradiol, baseline

impulsivity measures, etc. This pre-specified list will be determined by the study team during the finalization of the protocol, prior to the first study enrollment. We expect these analyses to be somewhat conservative, since they do not explicitly account for the randomized permuted blocking (Matts and Lachin, 1988). An analysis that accounts for the blocking (such as a stratified Mantel-Haenzel test) cannot be generalized to include the adjustment for impulsivity measures, for example, which are a focus of this proposal. All persons randomized and with a measured primary outcome at the week 4 visit will be included in this analysis, regardless of whether or not they ever took any of their assigned treatment (intent-to-treat analysis); persons with missed visits are discussed below.

Addressing Hypothesis 1a: An unadjusted assessment of the treatment effect will come from a linear model of percent reduction in marijuana use on randomized treatment assignment, separately by sex. **Hypothesis 1b:** A linear model including both males and females will be used to estimate the overall gender effect on percent reduction in marijuana use. **Hypothesis 1c:** A linear model including both males and females will be used to estimate the association of serum progesterone with percent reduction in marijuana use; we will separately consider baseline progesterone, cumulative progesterone (summed over weeks 0-4), and week 4 progesterone.

Addressing Hypothesis 2a: A linear model including both males and females will be used to estimate the association of impulsivity with percent reduction in marijuana use. **Hypothesis 2b:** A linear model including both males and females will be used to estimate the interaction between baseline impulsivity and baseline serum progesterone on percent reduction in marijuana use.

Missing data plan: Quality assurance plans are described below. The primary outcome analysis will be carried out using two parallel models: one model will exclude subjects for whom we were unable to obtain a week 4 TLFB or urine THC. Since 'missing at random' is a strong statistical assumption to make, we will also carry out a parallel model that uses multiple imputation of the week 4 TLFB and urine THC based on an individual's previous visits' TLFB and urine THC levels. We will also examine whether persons missing their week 4 visit differed in their baseline characteristics or treatment assignment from persons not missing their week 4 visit.

Power: This is a pilot study to generate data to potentially motivate and justify a future fully-powered study of PRO and marijuana use. This study will estimate magnitude and direction of treatment effects and associations with impulsivity (sex-specific and overall). Hence, no power calculations are provided.

Data Safety and Monitoring Plan, Board, and Administration.

The Admin Core Director ([name]) and the Statistical Analysis Core Director ([name]) of the P50 will jointly organize review by the Data Safety and Monitoring Board (DSMB). The Project PI ([name]) will administratively oversee complying with reporting requirements. The DSMB will meet annually and will, post meeting, provide a summary of discussion, which will be conveyed to NIDA. This report will include subject demographics, expected versus actual recruitment rates, summary of any quality assurance or regulatory issues, summary of adverse events (AEs) or serious adverse events (SAEs) which may have occurred, and any changes in the protocol as a result of these issues. The DSMB will receive current data and blinded data unless a specific request or cause to view un-blinded data is evident. The final report will be complete and inclusive with the unblended data set.

The Project Coordinator ([name]) and PI ([name]) will meet on a weekly basis to review the study's progress. The team will meet regularly and as needed regarding data and project safety. Additionally, all key personnel will meet regularly regarding overall progress, specific problems and problem resolution. The daily monitoring of subjects will be the coordinator's responsibility.

Participants will be closely monitored throughout the trial. A summary of all data, with the exception of information that entails breaking the blind, will be provided to the DSMB at annual meetings. SAE's will be reported to the head of the DSMB when they have been identified and characterized. The chair of the DSMB may request a special meeting of the panel as needed. The Board will consist of Drs. [name] (Chair), [name], [name], and an expert in marijuana abuse (TBN). These individuals will serve to monitor all the SCOR projects involving human subjects, including this project.

The group will meet on an annual basis and review data including recruitment, progress, safety, adverse events, and serious adverse events associated with the study. The DSMB meeting will include open, closed and executive sessions. The Principal Investigator, co-investigators, statisticians, and study coordinators will attend the open session and present during the meeting. The purpose of the open session is to provide relevant information to the Board about general aspects of the trial. The open session will focus on the background of the study, the protocol, status of the study, problems with accrual and follow-up, baseline demographic data, compliance issues, frequency of adverse events, documentation of endpoints, data quality issues, flow of forms, data based protocol modification issues, and any other issue regarding the studies under review that can be discussed without reference to interim comparative results.

Following the open session, a closed session will be held if deemed appropriate and necessary by the DSMB Chair. During the closed session, the chairperson ([name] MD) will conduct the review of all issues and puts each issue to a vote. This session will be attended by the DSMB members and if necessary the statistician and principal investigator. During the closed session, the discussions will focus on the treatment safety, requesting and reviewing additional information if needed and updating the Board on actions taken related to their actions and recommendations of the previous meeting.

Following the closed session, an executive meeting may be held, at the discretion of the DSMB Chair. The executive meeting will be restricted to DSMB members. During these sessions, the Board may discuss any sensitive issues surrounding the clinical trials under review.

The Board Chairperson will prepare a draft report of the meeting along with minutes for inclusion in the final DSMB report. The report will outline and summarize discussion during the open and closed sessions of the meeting. Recommendations and action items will be clearly marked within the body of the report. If the DSMB conducts an executive session, a statement will be included in the Minutes of the Meeting stating that an executive session was conducted, but content of the discussion will be retained by the chair and not included in the report. The draft report shall be reviewed and edited by all Board members prior to issuance of the final report.

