Inclusion: Males 18-60 years old, females 18-50 years old, stable physical and mental health, self-report Timeline Follow-Back (TLFB) indicating current marijuana use ≥4 days/week for ≥1 year, positive urine THC dipstick test ($> 50\text{ng/mL}$; indicating marijuana use in the past 48-72 hours), motivated to change their marijuana use (≥ 1 on a 10-point Likert-type scale), regular or sporadic use of nicotine cigarettes (> 1 cigarettes in the past 30 days), self-report of regular menstrual cycles ≥6 months (female only), willing to use double-barrier contraception if sexually active and not surgically sterilized (female only), ability to comply with study procedures, ability to provide informed consent.

Exclusion: Current breastfeeding (females only), current or planned pregnancy within the next three months (females only), DSM-IV diagnoses for psychotic disorders, bipolar disorder, ADHD, major depressive

disorder within the last 3 months, substance dependence within the last 3 months with the exception of nicotine and marijuana dependence, unstable psychotropic medications (<3 months), current use of exogenous hormones, finasteroid (propecia), efavirenz, red clover, ketoconazole and other drugs that are CYP3A4 inhibitors, conditions contraindicated to progesterone treatment (including, but not limited to, thrombophlebitis, deep vein thrombosis, pulmonary embolus, clotting or bleeding disorders, heart disease, diabetes, history of stroke, allergy to peanuts, hypersensitive to progesterone and liver dysfunction).

Visit Sequence & Procedures

Screening Visits (Visits 1 and 2): Candidates completing the consent process will be screened in a two-visit process (with the option of completing visits 1 and 2 simultaneously). For males, this two-visit process will be scheduled within two weeks of completion of the phone interview. For females, this two-visit process will be scheduled during the follicular phase of their menstrual cycle (in order to avoid any potential menstrual phase effects on marijuana use or mood measures, as well as to limit wait time for initial study procedures) (details below). Therefore, after the phone screen females will be told to contact the study coordinator with the first day of their next period, and then the two-part screening visits will be scheduled during days 1-7 (where Day 1 is the onset of menses) of the menstrual cycle.

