At the first of two screening visits (*Screening Visit 1*), the study will be described in detail to candidates by the study coordinator, and informed consent will be obtained. Subjects agreeing to participate will undergo medical, psychiatric and other evaluation to determine eligibility. The medical evaluation will include: brief physical exam (height, weight, blood pressure, heart rate, and medical history interview), psychiatric interview, carbon monoxide level and a blood draw (for measurement of serum hormone levels and liver function via ALT and AST measurement), a urine pregnancy test (females only) and a drug screening for marijuana (see *THC Urine Dipstick Test* for more information). Trained staff will conduct all interviews including the Structured Clinical Interview for DSM-IV (SCID; First, 1995) and instrument administration. Self-report instruments measuring impulsivity, personality characteristics, stress, caffeine use, tobacco use, marijuana use, craving and behavior will be completed. At the second screening visit (*Screening Visit 2*; scheduled within two days of Screening Visit 1), impulsivity tasks will be completed. The investigators will review the data to determine eligibility. Subjects meeting eligibility criteria will be given instructions on when to come back for their Baseline Visit (details below).

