Baseline Visit (Visit 3): Female subjects will be instructed to come into the clinic within three days of the start of their Luteal Phase for their baseline visit and to start medication (PRO or PBO). Female subjects will self-report menstrual cycle length at their screening visit and staff will determine when their Luteal Phase will most likely begin. Male subjects will be instructed to come into the clinic according to their assigned delay (per randomization list generated by the Statistical Analysis Core). This visit will occur seven days prior to quit date. At this visit, subjects will be randomized to PRO or PBO within strata defined by sex. The Statistical Analysis Core (SAC) will generate the randomization tables (one for each sex, 1:1 allocation using randomly permuted blocks of size 2 and 4), and the Clinical Trials Research Pharmacy will use it to determine randomization assignment. Randomization assignment will be stored in a secure file in a secure location at the Clinical Trials Research Pharmacy, to be shared only with the SAC. All other project staff including PI and study coordinator, as well as the participant, will remain blinded to the randomization assignment. At the baseline visit subjects will provide a blood sample (for hormone assessment), urine sample for THC, breath sample (to confirm smoking status via carbon monoxide breathalyzer), have their vital signs (blood pressure, heart rate, weight) measured, be informed of their quit date, and receive brief behavioral counseling to prepare for their quit date. At the end of this visit subjects will be compensated for their time, given study medication along with instructions for taking the medication (beginning at 8PM that day), as well as a clinic visit schedule for the remaining clinic visits. This visit will take approximately one hour to complete.

Marijuana Change Date Assignment: Change date (Week 0) will be set for 7 days following the Baseline Visit. Since this entails a delay of variable duration from Screening Visit 2 to Baseline Visit (thus impacting timing of medication initiation) across female subjects, each male subject will be matched to a female subject for a similar delay so that, across the male and female groups, study procedures will follow a similar chronology.

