- Weeks 0-5 (Visits 4-9):** The Week 0 clinic visit will occur on the assigned “Marijuana Change Date”. Subjects will attend clinic visits on a weekly basis thereafter for 5 weeks. At weeks 0, 2, 4, and 5, blood samples will be collected and stored for the analysis of hormones. Urine samples will be collected at each

clinic visit for the visual inspection of riboflavin (assessing medication compliance), biochemical confirmation of THC, and for a pregnancy test (females only). Urine will be saved and stored on Weeks 0, 2, 4, and 5 for cotinine analysis.

Subjects will also complete several forms and questionnaires (described below). Subjects will return the medication bottle and unused medication, be given a new one-week supply and adverse events will be assessed. At Week 4, subjects will complete impulsivity tasks and study medication will be discontinued. Finally, subjects will receive brief, behavioral counseling at each clinic visit. At the end of each visit subjects will be paid for their time. These visits will take approximately 30-45 minutes to complete.

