Serious Adverse Events (SAE): A serious adverse event is defined as an outcome that is 1) fatal or life-threatening, 2) significantly or permanently disabling or incapacitating, 3) requires or prolongs inpatient hospitalization, or 4) results in a congenital anomaly. SAE's, whether or not related to study medication, will be reported to the IRB and NIDA. All drug related adverse events of a non-serious nature are reported to the University of Minnesota's IRB on an annual basis. Serious adverse events will be reported by telephone to the IRB, and to NIDA and the FDA within the three days of our receipt of information regarding the event and written reports will be submitted within ten days. If a subject either withdraws from the study or the investigator decides to discontinue a subject due to SAE, the subject will have appropriate follow-up medical monitoring. Monitoring will continue until the problem requiring hospitalization was resolved or stabilized with no further change expected, is clearly unrelated to study medication, or results in death. Outcome of SAEs will be periodically reported to NIDA. A summary of the SAEs that occurred during the previous year will be included in the annual progress report to NIDA. Finally, the PI will ensure that serious adverse events are reported to NIDA via the serious adverse event tracking and reporting system at <https://saetr.snia.nih.gov/>.

The Principal Investigator will then take appropriate action (including study modification) as agreed upon by these monitoring groups including the DSMB when needed. The Principal Investigator will determine whether the seriousness of the event warrants removal of the participant from the study. Appropriate diagnostic and therapeutic interventions will be initiated and the participant will be medically followed and kept under observation as long as medically indicated. After the review of the data, the DSMB report will make recommendations about whether the trial should continue with or without modifications, or be terminated. Any potential conflict of interest in the Data and Safety Monitoring Board will be disclosed.

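### Pregnancy is an exclusion and is tested at screening and at every visit from Week 0, but no test is listed at the Baseline visit, where women are randomized and start drug

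*Combined protocol and SAP*

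**What the plan says.** All references are to the combined protocol and SAP.

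- **Exclusion criteria:** the list includes "current or planned pregnancy within the next three months (females only"). The inclusion criteria ask sexually active, non-sterilized women to be willing to use double-barrier contraception.
- **Screening Visit 1:** the medical evaluation includes "a urine pregnancy test (females only) and a drug screening for marijuana". For women, "the two-part screening visits will be scheduled during days 1-7 (where Day 1 is the onset of menses) of the menstrual cycle".
- **Baseline Visit (Visit 3):** women come in "within three days of the start of their Luteal Phase for their baseline visit and to start medication". The date is predicted, not measured: from self-reported cycle length, "staff will determine when their Luteal Phase will most likely begin". The specimens are itemised: "At the baseline visit subjects will provide a blood sample (for hormone assessment), urine sample for THC, breath sample". Vital signs and counseling follow. Randomization takes place at this visit, and the first dose is due at 8 PM the same day.
- **Weeks 0-5 (Visits 4-9):** urine is collected at each visit for the riboflavin compliance check, for "biochemical confirmation of THC, and for a pregnancy test (females only"). Week 0 is seven days after Baseline.
- **Table 1:** the urine row is labelled for THC and cotinine. The table has no pregnancy-test row for any visit.

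**The concern.** The plan does not treat one negative test plus contraception as enough, because it repeats the test at all six visits from Week 0 to Week 5. The visit that starts exposure is the exception. Read as written, a woman is randomized and begins blinded drug on the strength of a test done in the first week of her cycle, and the exclusion is not checked again until a week of dosing has passed.

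Two things are at stake. One is avoidable exposure of a woman whom the plan means to exclude. The other is a loss to the trial. A pregnancy found before randomization is an ordinary screening failure. Found at Week 0, it concerns a randomized participant. Under Study Adherence, if she then discontinues she is counted as incomplete and is not replaced. The target is 20 female completers, about 10 per arm, so each such loss is noticeable.

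**Working it through.** **Which visits carry a test**

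| Visit | Pregnancy test listed? | Stated use of urine |
|---|---|---|
| Screening Visit 1 | Yes | Pregnancy test; marijuana screen |
| Baseline (Visit 3) | No | THC |
| Weeks 0 to 5 (Visits 4-9) | Yes, each visit | Riboflavin, THC, pregnancy test; cotinine at Weeks 0, 2, 4 and 5 |

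The each-visit wording for Weeks 0-5 does not reach back to Baseline. It sits under a heading for Visits 4-9, and the same sentence covers a compliance check that makes sense only after dosing has begun. The Baseline section states separately what its urine is for.

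**Age of the last listed test at first dose**

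Inputs from the protocol: test on cycle day 1 to 7; Baseline within three days of luteal start, taken here as 0 to 3 days after it; first dose on the evening of Baseline; Week 0 seven days later. Assumptions, not in the protocol: a 14-day luteal phase, and cycle lengths of 21 to 35 days.

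- Predicted luteal start day = cycle length − 14 + 1.
- Shortest gap = luteal start − 7. Longest gap = luteal start + 3 − 1.
- Interval from the screening test to the Week 0 test = gap + 7.

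For 28 days: luteal start = 28 − 14 + 1 = day 15; shortest gap 15 − 7 = 8; longest gap 15 + 3 − 1 = 17; interval to the Week 0 test 15 to 24 days.

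| Cycle (days) | Luteal start (day) | Test to first dose (days) | Screening test to Week 0 test (days) |
|---|---|---|---|
| 21 | 8 | 1 to 10 | 8 to 17 |
| 24 | 11 | 4 to 13 | 11 to 20 |
| 28 | 15 | 8 to 17 | 15 to 24 |
| 32 | 19 | 12 to 21 | 19 to 28 |
| 35 | 22 | 15 to 24 | 22 to 31 |

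If the three-day window is read as either side of luteal start, the lower limit of each gap falls by 3 (for 28 days, 5 to 17). For every cycle length tried, the latest screening day (7) comes before the predicted luteal start.

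**Doses before the next listed test**

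One evening dose at Baseline, two a day for the next six days, and the morning dose on the day of Week 0: 1 + 6 × 2 + 1 = 14. It is 13 if the last is taken after the visit.

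**Women concerned**

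The plan enrolls 35 women. With 1:1 allocation, about 35 / 2 = 17 to 18 receive active drug.

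**The case against.** Much of the case on the other side stands, and it limits the size of the point.

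- **Yield.** A reader might infer that a Baseline test would cover the fertile window between screening and Week 0. It generally would not. As a matter of general physiology, a urine test around luteal onset is too early to detect a conception in that same cycle. Its main use is to catch a pregnancy missed at screening, for example when bleeding was mistaken for menses, or one in a woman whose cycle was misdated.
- **Existing safeguards.** Screening is timed to reported menses and includes a test. Planned pregnancy is excluded, double-barrier contraception is required where relevant, all women are educated about it, and tests resume at Week 0. The residual risk is small. Some of the 35 women may be sterilized or not sexually active, and about half receive placebo.
- **Weak evidence from Table 1.** It has no pregnancy row even for visits where the text requires the test, and it omits riboflavin, carbon monoxide and vital signs. The Baseline narrative is not exhaustive either; Table 1 places questionnaires there that it does not mention. The finding therefore rests on the visit descriptions. Staff may test at Baseline in practice, and the consent form, which is not available here, may say so.
- **A gap, not a contradiction.** Eligibility is settled after screening, and the text does not promise to recheck exclusions at Baseline. That is correct. The inconsistency is with the plan's own pattern of testing.
- **Fetal outcomes.** The SAE definition includes an event that "results in a congenital anomaly", and visits end at Week 5, so a reader might infer that this criterion could never be observed. The documents do not support that. The Adverse Events section commits the investigators to follow all AEs to satisfactory resolution, and the SAE section keeps a participant under observation as long as medically indicated. Pregnancy is not named there, but follow-up is not closed at Week 5.

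**Conclusion.** The point holds as a modest safety and eligibility gap that should be fixed. As written, the plan's own pregnancy exclusion is not verified at the visit where women are randomized and exposure begins. The absence of a listed test is a matter of text and needs no assumption. The age of the last test, 8 to 17 days at first dose for a 28-day cycle and 4 to 13 up to 15 to 24 days for cycles of 24 to 35 days, rests on the assumed 14-day luteal phase and on self-reported cycle length. The figure of about 14 doses before the next listed test follows from the stated schedule. The number of pregnancies that a Baseline test would find is likely to be small and cannot be estimated from the documents. The analysis plan is unaffected, except through the possible loss of a randomized woman who is not replaced.

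**What to change.** Reconcile the exclusion criteria, the Screening, Baseline and Weeks 0-5 descriptions, and Table 1. Apply the pregnancy check already used at the other visits to the urine already collected at Baseline, with the result available before randomization, so that the plan's own exclusion is verified at entry. Add a pregnancy-test row to Table 1 showing every visit at which the test is done. What happens to study medication after a positive test is for the sponsor to state.

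The cost is up to about 35 dipsticks, a few minutes per visit and a few lines of text. The downside is that an occasional woman will be excluded late, after waiting for her Baseline date.
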